4 ENDPOINTS

4.1 Primary Endpoint

- The primary efficacy endpoint is the proportion of subjects in Renal Response (defined in [Section 8.1.1](#)) at Day 113.

4.2 Secondary Efficacy Endpoints

- Mean change from baseline in UPCR at Day 113.
- Mean change from baseline in serum albumin at Day 113.
- Proportion of subjects achieving complete remission ($UPCR \leq 0.3$ with eGFR: normal or $\geq 75\%$ of baseline value if below normal at baseline) at Day 113.
- Mean change from baseline in PROMIS measures at Day 113.

4.3 Safety Endpoints

- All adverse events (AEs, SAEs, AEs leading to discontinuation, deaths, etc.).
- AEs of interest (infections, malignancies, autoimmune disorders, infusional related reactions, renal-related events).

4.4 Laboratory test abnormalities. Immunogenicity Endpoints

- Proportion of subjects with positive antibody response relative to baseline over time.

[REDACTED]

5 SAMPLE SIZE AND POWER

This pilot study is planned to randomize approximately 90 subjects to assess the primary endpoint of proportion subjects in Renal Response at Day 113 between the abatacept and placebo arms. The randomization will be stratified by Genotype for whom test results, obtained either prior to enrollment or at screening, are available (APOL1 high risk group vs. Others) and Age (< 18 y and ≥ 18 y).

A total of 90 subjects randomized in a 1:1 ratio to abatacept vs. placebo will yield approximately 80% power to detect a treatment difference (delta) of 28% between the two treatment arms. This power estimate assumes a 2-sided alpha level of 5%, and Renal Response rate of 40% and 12% in the abatacept and placebo arms respectively. The 12% estimate of Renal Response in the placebo arm was based on observed rate of Renal Response in the FONT II study³ which has a similar population that is proposed for the present study and expert opinion.

6 STUDY PERIODS, TREATMENT REGIMENS AND POPULATIONS FOR ANALYSES

6.1 Study Periods

In this study, there are four study periods: screening period, double-blind period (DB), open label extension period (OLE), and follow-up period.

The following analysis periods defined below are for analysis purposes. The definitions below indicate the data to be included in the analysis of each specified period. Subjects discontinued during a specified period (DB or OLE) will be considered on-treatment for 56 and 42 days after the last dosing in that period for safety and efficacy analysis respectively. Follow-up period data will be included in one of the analysis periods depending on the time of completing the study.

Screening Period: Starts with the day of enrolment and ends prior or on the day of first dose of study medication (abatacept or placebo).

Double-Blind Period: Starts with the first dosing of double-blind study medication and ends 56/42 days (for safety/efficacy analysis) after the last dose of the double-blind period or the first dosing of OLE, whichever is earlier.

For subjects who completed Period 1 and entered Period 2 prior to Protocol Amendment 2, includes data from first dose date in Period 1 up to the first dose in Period 2.

Open Label Extension Period (OLE): Starts with the first dosing in the OLE and ends 56/42 (for safety/efficacy analysis) days after the last dose in the OLE.

Cumulative Abatacept Safety Period: Starts at the time of the first dose of abatacept (either in the double-blind period for the subjects randomized to abatacept or in the OLE for the subjects randomized to placebo) and continues up to 56 days post last dose of abatacept for safety (AE and laboratory summaries). The last abatacept dose can be last dose in double-blind period for subjects not treated in the OLE.

For subjects who completed Period 1 and entered Period 2 prior to the protocol revision:

- For subjects on abatacept during Period 1:
 - For subjects who do not enter OLE period: starts with the first dosing of Period 1 and ends 56 days after the last dosing of Period 1.
 - For subjects who enter OLE period: starts with the first dosing of Period 1 and ends 56 days after the last dosing of Period 1 combined with OLE period that starts with the first dosing in the OLE period and ends 56 days after the last dosing in the OLE period.
- For subjects on placebo during Period 1:
 - For subjects who do not enter OLE period: starts with the first dosing of Period 2 and ends 56 days after the last dosing of Period 2.
 - For subjects who enter OLE period: starts with the first dosing of Period 2 and ends 56 days after the last dosing of OLE period. If a subject's first dosing in OLE period is more than 56 days from last dosing in Period 2, the duration after 56 days from last dosing in Period 2 to the first dosing in OLE will be excluded.

6.2 Treatment Regimens

There are two treatment groups: abatacept IV or placebo IV. Abatacept IV will be dosed based on age group and weight as follows:

- Adults (≥ 18 years):
 - $< 60\text{kg}$: 500mg
 - $60 - 100\text{kg}$: 750mg
 - $> 100\text{kg}$: 1000mg
- Pediatric (6-17 years):
 - $< 75\text{kg}$: 10mg/kg
 - $\geq 75\text{kg}$ follow adult dosing

6.3 Populations for Analyses

Efficacy endpoints will be summarized according to the Intent-to-Treat (ITT) population and safety endpoints will be summarized according to the As-Treated population. These populations are described below along with the Per-Protocol population, Immunogenicity population and the Pharmacokinetic population

6.3.1 *Intent-to-Treat Analysis Population*

The Intent-to-Treat (ITT) Analysis Population is defined to include all subjects randomized into the study for whom Case Report Form (CRF) data indicate that at least one dose of study medication (abatacept or placebo) was administered during the double-blind period.

All subjects who were randomized but never received study medication are to be excluded. Given the blinded nature of this study, it is reasonable to assume that subjects who discontinue prior to the receipt of study medication do so for reasons unrelated to study medication.

Subjects are grouped according to the treatments to which they are randomized by Interactive Response System (IxRS).

ITT Analysis Population is also referred to as ‘All Randomized and Treated Subjects’.

6.3.2 *As-Treated Analysis Population*

The As-Treated Analysis Population contains all subjects for whom CRF data indicate that at least one dose of study medication was administered during double-blind period.

Subjects are grouped according to the treatments to which they are randomized, except in cases where information is available, which indicate that a subject received a different treatment for the entire course of the 16 week double-blind period. In this case, the subject will be presented by the treatment they actually received.

The As Treated Analysis Population will also be referred as ‘All Treated Subjects’.

6.3.3 *Per-Protocol Analysis Population*

The Per-Protocol Analysis Population is defined as a subset of the ITT Analysis Population which excludes subjects who have relevant protocol deviations during the 16 week double-blind period. A programmable list of relevant protocol deviations is provided in [APPENDIX 1](#).

The Per-Protocol Analysis Population will only be used if more than 10% of the subjects in either treatment group have relevant protocol deviations. In such a case, the analysis of the primary efficacy endpoints will be repeated in the Per-Protocol Analysis Population.

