8.2 Populations for Analyses

Efficacy endpoints will be summarized according to the **Intent-to-Treat (ITT)** population and safety endpoints will be summarized according to the **As Treated** population. These populations are described below along with the Per-Protocol population and the Immunogenicity population.

Intent-to-Treat Analysis Population

The Intent-to-Treat (ITT) Analysis Population is defined to include all subjects randomized into the study for whom Case Report Form (CRF) data indicate that at least one dose of study medication (IV Abatacept or placebo) is administered during the Double-Blind Period.

All subjects who are randomized but never received study medication are to be excluded. Given the blinded nature of this study, it is reasonable to assume that subjects who discontinue prior to the receipt of study medication do so for reasons unrelated to study medication.

Subjects are grouped according to the treatments to which they are randomized by the Central Randomization System (IV Abatacept vs placebo).

ITT Analysis Population is also referred to as ‘All Randomized and Treated Subjects’.

As-Treated Analysis Population

The As-Treated Analysis Population contain all subjects for whom CRF data indicate that at least one dose of study medication was administered during the Double-Blind Period.

Subjects are grouped according to the treatments to which they are randomized, except in cases where information is available, which indicate that a subject receives a different treatment for the entire course of the 16 week Double-Blind Period. In this case, the subject will be presented by the treatment they actually received.

The As Treated Analysis Population will also be referred as ‘All Treated Subjects’.

Per-Protocol Analysis Population

The Per-protocol Analysis Population is defined as a subset of the ITT Analysis Population which excludes subjects who have relevant protocol deviations during the 16 week double-blind period. A programmable list of relevant protocol deviations will be included in the Statistical Analysis Plan and approved prior to the database lock for the 16 week Double-Blind period.

The Per-protocol Analysis Population will only be used if more than 10% of the subjects in either treatment group have relevant protocol deviations. In such a case, the analysis of the primary efficacy endpoints will be repeated in the Per-protocol Analysis Population.

Immunogenicity Analysis Population

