7.2 Study Conduct

Relevant protocol deviations, which could have major impact on the interpretation of the primary efficacy endpoint of the study results, will be identified prior to the unblinding the database for all subjects who are randomized and receive double-blind medication. Relevant protocol deviation criteria are listed in [APPENDIX 1](#).

All relevant protocol deviations, pre-randomization and during double-blind period, will be listed and summarized by treatment arm. The per-protocol analysis population will exclude subjects with at least 1 relevant protocol deviation. Relevant protocol deviations will not be assessed for the OLE analysis.

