7.5 Efficacy

The primary and secondary efficacy analyses (defined in [section 7.5.2](#) and [7.5.4](#)) will be performed using the ITT Analysis Population by treatment group assigned at randomization during the double-blind period. The primary analysis will be repeated using the PP analysis population if more than 10% of subjects in any treatment group meet the criteria for a relevant protocol deviation. All other efficacy analyses will be performed using the ITT Analysis Population, unless otherwise specified.

The efficacy analysis in this analysis plan is mainly focused on the double-blind period.

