APPENDIX 2 RELEVANT PROTOCOL DEVIATIONS

Pre Randomization:

- UPCR < 2.7 at screening.
- eGFR below the following level at screening:
 - 50 for subjects < 18 years (new Schwartz equation).
 - 50 for subjects ≥ 18 years (CKD-EPI equation).
- Body mass index (BMI): > 45 in subjects ≥ 18 years of age and ≥ 99% percentile for subjects < 18 years of age at screening.
- Hemoglobin (Hgb) < 7.0g/dl at screening.
- White Blood Count (WBC) < 2,000/mm³ (2 x 10⁹/L) at screening.
- Platelets < 75,000/mm³ (75 x 10⁹/L) at screening.
- Serum ALT or AST > 3 times upper limit of normal at screening.
- Subjects systemically using any of CS (low dose, prednisone or equivalent at doses ≤ 15mg/day), calcineurin inhibitors (cyclosporine and tacrolimus), MMF and MPA for treatment of TRNS (use for other medical indications [e.g. asthma] is allowed), satisfying any of the following:
 - Started using one of the above agents within 8 weeks of enrollment.
 - Not using the standard dose or
 - Have not been on stable dose for at least 4 weeks prior to randomization.

Post Randomization:

- FSGS or MCD diagnosis not confirmed by a pathology report.
- Use of prohibited medication:
 - Any systemic immunosuppressive or immunomodulator per protocol including, but not limited to cyclophosphamide, methotrexate, belimumab, azathioprine, leflunomide, rituximab, experimental therapies, everolimus, sirolimus, corticotropin injection gel (ACTH) or plasmapheresis.
 - Combined use of two or more renin-angiotensin system (RAS) inhibitors.
- Missed two or more doses of investigational product for any reason during double-blind period.

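### Per-protocol membership has two answers: SAP 6.3.3 and Protocol 8.2 count only double-blind deviations, while SAP 7.2 counts pre-randomization deviations as well

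*SAP*

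**What the plan says.** **Definition of the set.** SAP 6.3.3 takes the ITT population and forms a subset "which excludes subjects who have relevant protocol deviations during the 16 week double-blind period". Protocol 8.2 has the same limit: the set "excludes subjects who have relevant protocol deviations during the 16 week double-blind period". The protocol leaves the list of deviations to the SAP.

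**Study conduct.** SAP 7.2 has a wider scope: "All relevant protocol deviations, pre-randomization and during double-blind period, will be listed and summarized by treatment arm". The next sentence gives a membership rule without any time limit: "The per-protocol analysis population will exclude subjects with at least 1 relevant protocol deviation".

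**The list.** SAP Appendix 2 has a pre-randomization block, with items such as "UPCR < 2.7 at screening", and a post-randomization block, with items such as "Missed two or more doses of investigational product for any reason during double-blind period". SAP 6.3.3 and 7.2 both send the reader to Appendix 1 for this list, but Appendix 1 is the document history.

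**When the set is used.** SAP 6.3.3 says it "will only be used if more than 10% of the subjects in either treatment group have relevant protocol deviations". SAP 7.5 repeats the primary analysis in this set "if more than 10% of subjects in any treatment group meet the criteria for a relevant protocol deviation".

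**The concern.** Two programmers working from this SAP could build different per-protocol flags, and each could point to a sentence in support. No sentence says that 7.2 overrides 6.3.3 or the reverse. All the sentences are current text, so the amendment history does not explain the difference.

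The per-protocol analysis is the only planned repeat of the primary analysis in a different analysis population. The sensitivity analysis in SAP 7.5.2 stays in the ITT population and only drops genotype from the model. If the membership rule is chosen after unblinding, the choice could be influenced by which set gives the more convenient result. SAP 7.2 requires deviations to be identified before unblinding. That fixes who has which deviation, but not which deviations lead to exclusion.

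**Working it through.** **1. The plan's own numbers.** SAP section 5 gives 90 subjects randomized 1:1, so 45 per arm, with about 80% power for 40% versus 12% at two-sided 5%.

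- Without continuity correction, n = [1.960·√(2·0.26·0.74) + 0.842·√(0.40·0.60 + 0.12·0.88)]² / 0.28² = 37.3, or 38 per arm.
- With the correction, n = (37.3/4)·[1 + √(1 + 4/(37.3·0.28))]² = 44.2, or 45 per arm.

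The stated size reproduces, and nothing below changes it.

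**2. The Appendix 2 items.**

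- Pre-randomization, 8 items: screening UPCR, eGFR, BMI, hemoglobin, white cells, platelets, ALT/AST, and background therapy (recent start, non-standard dose or unstable dose).
- Post-randomization, 3 items: diagnosis not confirmed by a pathology report, prohibited medication, two or more missed doses.

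The total is 11. A double-blind-only rule leaves 8 of the 11 with no role in membership. The block headings are not a clean guide to timing either. Unconfirmed diagnosis is filed as post-randomization, although Protocol 5.2.9 requires central confirmation before a subject qualifies for randomization.

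**3. The two rules side by side.**

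| Treated subject | SAP 6.3.3 / Protocol 8.2 | SAP 7.2 |
|---|---|---|
| No listed deviation | in | in |
| Two missed double-blind doses | out | out |
| Entry deviation only (e.g. screening UPCR below 2.7) | in | out |

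The third row is the conflict.

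**4. The trigger.** The rule is k/n > 0.10. With n = 45, 4/45 = 8.9% does not meet it and 5/45 = 11.1% does, so five subjects in one arm suffice. The same count of five holds for any arm of 40 to 49 treated subjects (4/40 = 10.0% is not above 10%; 5/49 = 10.2% is).

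**5. How much the scope could matter to the trigger.** The documents give no deviation rates, so those below are assumptions. Let d be the share of subjects with a double-blind deviation and r the share with a pre-randomization deviation, independent and equal in both arms, with 45 per arm. The combined rate is q = 1 − (1 − d)(1 − r). The chance that at least one arm triggers is 1 − [1 − P(X ≥ 5)]², with X binomial (45, d) or (45, q).

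| d | r | q | Counting double-blind only | Counting both |
|---|---|---|---|---|
| 3% | 5% | 7.85% | 2% | 48% |
| 5% | 5% | 9.75% | 14% | 70% |
| 8% | 5% | 12.6% | 50% | 90% |

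**6. A side effect of the wider scope.** Protocol 3.3.1 admits subjects with a screening eGFR of 45 or above, both under and over 18 years. Appendix 2 flags a screening eGFR below 50 as a relevant deviation. A subject between 45 and 50 is therefore eligible under the protocol, yet is removed from the per-protocol set under SAP 7.2 and counted toward the trigger. The other laboratory cut-offs in Appendix 2 are looser than the eligibility limits: UPCR 2.7 against 3, hemoglobin 7.0 against 8.5 g/dL, white cells 2,000 against 3,000/mm³, platelets 75,000 against 100,000/mm³, ALT/AST 3 against 2 times the upper limit.

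**The case against.** The best defence is that the intended rule can be recovered. The sentence after the definition in 6.3.3 points to the list, the list has a large pre-randomization block, and 7.2 states an operational rule after naming both periods. The narrow phrase looks like protocol wording carried over. I agree that the wider scope was probably meant. Even so, the section that defines the population says otherwise, the protocol agrees with that section, and no rule of precedence is given.

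The second defence concerns the trigger, and much of it stands. A reader might infer that five entry deviations in one arm count as 0% under 6.3.3 and 11.1% under 7.2, so that the trigger itself gives two answers. The documents do not go that far. Neither trigger sentence has a time limit; 7.5 refers simply to meeting the criteria for a relevant deviation, and taken literally both give 11.1%. The 0% result appears only if the limit in the definition is carried forward into the next paragraph. That reading is open but not stated, and five entry deviations with none on study is a hypothetical case.

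A reader might also infer that the narrow rule keeps subjects who never had disease severe enough for the endpoint. A screening UPCR below 2.7 does not show that. Only one of the eight entry items concerns UPCR, and response is judged against baseline, normally Day 1 (SAP 8.3).

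Finally, the analysis is a conditional repeat with no decision attached. That is correct, and it limits the importance of the point.

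**Conclusion.** The conflict over membership is established by the text alone. SAP 6.3.3 and Protocol 8.2 keep treated subjects whose only relevant deviation precedes randomization, and SAP 7.2 removes them. The number of subjects affected cannot be known from the documents.

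For the trigger the conclusion is weaker: its wording favours counting every listed deviation, but its position under the narrower definition leaves a second reading open. At five subjects per arm (assuming 40 to 49 treated in that arm), a few entry deviations could decide whether the analysis is run. The trigger probabilities rest wholly on assumed rates and independence, and show sensitivity rather than expectation.

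The ITT primary analysis, the type I error and the sample size are not touched. This is a clarification worth making before unblinding, not a threat to the trial's main result.

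**What to change.** Before unblinding:

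1. Reword SAP 6.3.3 so that the per-protocol set excludes ITT subjects with any relevant deviation listed in Appendix 2, whether before randomization or during the double-blind period.
2. State in 6.3.3 and 7.5 that the 10% trigger counts the same subjects.
3. Note in the SAP that this clarifies Protocol 8.2.
4. Change the Appendix 1 references in 6.3.3 and 7.2 to Appendix 2.
5. Reconcile the Appendix 2 eGFR cut-off (below 50) with the protocol entry limit (45 or above), so that subjects who met the entry limit are not counted as deviators. Without this step, item 1 would settle the scope but remove eligible subjects from the set.

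The cost is a few sentences in one SAP revision and one check of the deviation flag. It needs no new data and no change to the primary analysis.

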6.3.4 Immunogenicity Analysis Population

The Immunogenicity Analysis Population includes subjects who received at least 1 dose of abatacept and had an immunogenicity result available during the double-blind period.

6.3.5 PK Analysis Population

The PK Analysis Population includes subjects who received at least 1 dose of abatacept and had a measurable concentration result available during the double-blind period.

7 STATISTICAL ANALYSES

The randomization is stratified by Genotype (APOL1 high risk group vs. Others) and Age (< 18 y and \geq 18 y). Therefore genotype and age, which will be obtained from IxRS data, will be included as stratification factors in some of the efficacy analyses described below. The analyses to be performed at the end of study on OLE period is outlined in [Section 9](#).

7.1 General Methods

All construction of CIs for differences in response rates between treatment groups will be based on minimum risk weights⁴ to account for randomization stratification factors, unless otherwise noted. All construction of CIs for response rates within treatment group will be based on normal approximation, unless otherwise noted.

All construction of CIs for continuous measures will be based on a mixed effects model which includes treatment group, baseline value of variable, randomization stratification factors, time, time by treatment interaction, and baseline value by time interaction as fixed effects and subject as a random effect. An unstructured covariance matrix will be used to model the correlation of the repeated measures within each subject. The SAS procedure PROC MIXED will be used with the restricted maximum likelihood (REML) method for estimation and the denominator degrees of freedom will be calculated according to the Kenward Roger method. In case of non-convergence of the preferred longitudinal model, memory space issues or other computational issues the following back-up models are defined:

- In the first backup model, the repeated statement will specify a spatial power covariance matrix and intercept and slope will be specified as random effects on a subject level.
- In the second backup model, the model will not include terms for the interaction between the baseline variable and time.

Unless otherwise specified, summary statistics will include the following:

- Summary statistics for continuous variables will include means, standard deviations, median, quartiles, minima and maxima.
- Summary statistics for qualitative or discrete variables will include the count and percentage.

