3.2 Secondary Objectives

- 1) Assess improvement in change from baseline in the level of proteinuria following treatment with abatacept compared to placebo.
 - Assess difference in mean change from baseline in Urine Protein/Creatinine Ratio (UPCR) at Day 113.
- 2) Assess improvement in serum albumin levels following treatment with abatacept compared to placebo.
 - Assess difference in mean change from baseline in serum albumin at Day 113.

- 3) Assess improvement in complete remission while maintaining renal function following treatment with abatacept compared to placebo.
 - Assess difference in percent of subjects achieving complete remission ($UPCR \leq 0.3$) with preservation of eGFR at Day 113.
- 4) Assess improvement in patient reported outcomes related to nephrotic syndrome.
 - Assess changes using the Patient Reported Outcomes Measurement Information System (PROMIS) at Day 113.
- 5) Assess the safety and immunogenicity of abatacept in subjects with TRNS.
 - Describe rates of AEs and SAEs and immunogenicity testing.
- 6) Assess the pharmacokinetics of abatacept in subjects with TRNS.
 - Describe the pharmacokinetics of abatacept.

[REDACTED]

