7.5.1 Analysis of Primary Efficacy Endpoint

The primary objective of the study is the comparison of renal response, defined by composite renal index, at Day 113 at the end of double-blind period between abatacept and placebo arms. The definition and computation method for renal response is provided in [Section 8.1.1](#).

The primary comparison of proportion of subjects in renal response at Day 113 at the end of double-blind period between abatacept and placebo arms will be assessed using a logistic regression model. The logistic regression model will adjust for baseline UPCR, baseline eGFR and the randomization stratification variables of Genotype (APOL1 high risk group vs. Others) and Age (< 18 y vs. ≥ 18 y). Point estimate of the adjusted Odds Ratios (OR) of the odds of achieving renal response in the abatacept arm compared to the placebo arm, corresponding 95% CI and p-value, will be provided. Unadjusted point estimate of the proportion of renal response in each treatment arm and corresponding 95% CI will also be provided. All subjects who discontinue prematurely prior to reaching the primary endpoint, and subjects with missing data for response at Day 113 assessment visit, will be considered as not achieving response in the primary analysis. The primary analysis will be based on the ITT Analysis Population.

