- The proportion of subjects achieving complete remission (defined in [Section 8.1.2](#): UPCR ≤ 0.3 with eGFR normal or $\geq 75\%$ baseline if below normal at baseline) at Day 113: the comparison in proportion of subjects achieving complete remission between the abatacept and placebo arms will be assessed using a logistic regression model. To account for randomization stratification, the logistic regression model will adjust for the randomization stratification variables of genotype and age in addition to adjusting for baseline UPCR and baseline eGFR. Point estimate of the adjusted Odds Ratios (OR) of the odds of achieving complete remission in the IV abatacept arm compared to the placebo arm, corresponding 95% CI, will be provided.
- Mean change from baseline in PROMIS measures at Day 113. Descriptive summary statistics for changes in patient reported outcomes of physical function, fatigue and pain improvement from baseline over time during double-blind period for the PROMIS static short forms will be provided by age group.

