8.2 Determination of Responders

For analyses of treatment differences in the proportions of subjects achieving a renal response or complete remission at specific time point, a conservative approach will be taken for subjects who prematurely discontinue prior to achieving the efficacy endpoint. That is, regardless of treatment group, these discontinued subjects will be considered as non-responders. Subjects with any missing renal response component will also be considered as non-responders.

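### Minor: the normal-approximation 95% CIs for the arm-level renal response rates cover about 91% at the planned placebo rate; a score or exact interval corrects this at almost no cost

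*SAP*

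**What the plan says.** SAP 7.1 sets the default: "All construction of CIs for response rates within treatment group will be based on normal approximation, unless otherwise noted". For renal response, SAP 7.5.1 then requests the arm-level figures: "Unadjusted point estimate of the proportion of renal response in each treatment arm and corresponding 95% CI will also be provided". It notes no exception, so the default applies. Protocol 8.4.2.1 asks for the same arm-level intervals and also names no method.

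The planning values in SAP section 5 are 90 subjects randomized 1:1 and a "Renal Response rate of 40% and 12% in the abatacept and placebo arms respectively".

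The SAP has one small-count rule for proportions. In 7.5.5 (Subgroup Analysis), the CI for the difference between arms within a subgroup uses the normal approximation only if each arm has at least 5 events, and an exact method otherwise.

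**The concern.** The Wald interval is centred on the observed proportion and takes its width from it. When few responders are observed, the estimate is low and the interval is also too short, so it tends to stop below the true rate. An arm of about 45 with an expected rate of 12% (5.4 responders expected) is in that territory.

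At stake is the accuracy of the error bars printed next to the primary result, above all for placebo. A reader would take them as 95% intervals and might use the placebo interval as a benchmark for later trials in this disease. In some outcomes the interval would also look wrong on the page, with a negative lower limit.

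**Working it through.** **Inputs.** Total 90, 1:1, so n = 45 per arm; 12% placebo, 40% abatacept; two-sided 5% (SAP 5). Subjects with missing data count as non-responders and stay in the denominator (SAP 8.2). Subjects never dosed leave it (SAP 6.3.1), so n could be a little under 45.

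**The plan's own figure first.** For 40% vs 12% at 80% power, the usual two-proportion formula gives [1.96·√(2·0.26·0.74) + 0.842·√(0.40·0.60 + 0.12·0.88)]² / 0.28² = 37.3 per arm. The continuity correction, (37.3/4)·[1 + √(1 + 4/(37.3·0.28))]², raises this to 44.2, so 45 per arm and 90 in total. Continuity-corrected power at 45 per arm is 80.9%, which matches the stated 80%. The planning figures are sound and are the right place to evaluate the intervals.

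**Wald interval.** p̂ ± 1.96·√(p̂(1−p̂)/n), with p̂ = x/45. Find the responder counts x whose interval misses 0.12:

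- x = 2: p̂ = 0.0444, standard error 0.0307, interval −0.016 to 0.105. It lies below 0.12, as do those for x = 0 and x = 1.
- x = 3: −0.006 to 0.140. Covers.
- x = 11: 0.119 to 0.370. Covers.
- x = 12: 0.138 to 0.396. It lies above 0.12, as do those for larger x.

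With X ~ Binomial(45, 0.12):

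- P(X ≤ 2) = 0.0032 + 0.0195 + 0.0584 = 0.0811
- P(X ≥ 12) = 0.0056
- Coverage = 1 − 0.0811 − 0.0056 = 0.9133
- Share of misses below the truth = 0.0811/0.0867 = 93.5%

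**Comparison at n = 45.** Wilson is [p̂ + z²/2n ± z·√(p̂(1−p̂)/n + z²/4n²)] / (1 + z²/n). Clopper-Pearson inverts the exact binomial tails.

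| True rate | Wald | Wilson | Clopper-Pearson |
|---|---|---|---|
| 12% | 91.3% | 93.9% | 96.2% |
| average over 10–14% | 91.5% | 95.3% | 97.2% |
| 40% | 93.0% | 95.3% | 96.6% |
| average over 30–50% | 93.9% | 95.0% | 96.5% |

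**Sensitivity.** Coverage of binomial intervals jumps with small changes in n and rate, so one point should not carry the argument alone. At 12%, Wald covers 86.8% with n = 40, 88.5% with 42, 89.8% with 44 and 92.9% with 48. With n = 45 it ranges from 87.6% to 93.6% at the true rates checked between 8% and 15%. It was below 95% at every one of these points. At 40% the picture is milder and less steady: 93.0% with n = 45, but 95.5% with n = 44. The average over 30–50% is the fairer summary there.

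**What the output can look like.** With 1 to 3 responders the Wald lower limit is negative (3/45: −0.6% to 14.0%; Wilson 2.3% to 17.9%). With none, the interval collapses to 0–0%, though that has probability only 0.3% at 12%. P(X ≤ 3) = 0.0811 + 0.1142 = 0.195. At the expected count the shift is plain too: 5/45 gives 1.9–20.3% by Wald and 4.8–23.5% by Wilson.

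**The case against.** Four points can fairly be made for the plan.

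1. **These are descriptive lines in a pilot study.** That is right, and it sets the weight of the point. Inference rests on the adjusted logistic regression. A reader might infer that the primary result is undermined; it is not.

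2. **The SAP already has a small-count device in 7.5.5.** Borrowed for the arm-level CI (Clopper-Pearson below 5 events, Wald otherwise), that threshold gives 97.2% coverage at 12% with n = 45, so it would cure the placebo arm. But 7.5.5 is worded for differences between arms within subgroups, and nothing carries it to 7.5.1. At 12% the whole placebo arm has fewer than 5 responders with probability 0.195 + 0.164 = 35.9%, and no rule then applies to its interval. Extending it would also leave the abatacept arm at 93.0%. One might read the two sections as contradicting each other. They do not; the SAP simply uses a safeguard in one place and not in the other.

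3. **The SAP gives no formula.** The 91.3% depends on reading normal approximation as Wald. A Wald interval with a 0.5/n continuity correction gives the same 91.3% at this point. If a Wilson score interval was meant, coverage is 93.9% and the remedy is only to say so. This condition stands.

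4. **Wilson also misses 95% at exactly 12%.** True: the gain there is 2.6 points. Averaged over 10–14%, however, it is 95.3% against 91.5%, and its misses at 12% are less lopsided (2.3% below, 3.8% above). Clopper-Pearson stays at or above nominal throughout.

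**Conclusion.** The point holds, as a minor one. As written, the arm-level CIs for renal response fall short of 95%: 91.3% at the planned placebo rate (91.5% on average over 10–14%), with nearly all misses below the truth, and 93.0% at 40% (93.9% on average over 30–50%). This assumes the Wald reading, 45 analysed per arm and true rates near the planning values. The 91.3% figure belongs to the placebo arm and should not be quoted for both.

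The effect stops at descriptive intervals. The primary odds ratio, its CI and p-value, the type I error and the power are untouched.

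A reader might go further and infer a similar sparse-data failure in the complete remission model of 7.5.3, since an arm with no remissions would make a maximum-likelihood odds ratio non-finite. The documents do not support making that a finding. They give no remission rate, so the risk cannot be sized from them. SAP 7.5 also cites a section 7.5.4 that is not in the text available, so the absence of a fallback cannot be asserted. The endpoint is secondary and carries no p-value.

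**What to change.** In SAP 7.1, replace the normal approximation for within-arm response rates with a named method, either Wilson score or Clopper-Pearson. Section 7.5.1 then inherits it without further change. If a score interval was intended all along, the same sentence makes that explicit.

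The cost is one sentence, with no change to design, sample size or primary model. At 12% the mean half-width is 9.2 points for Wald, 9.4 for Wilson and 10.2 for Clopper-Pearson. So Wilson costs about 0.2 points, and Clopper-Pearson about 1 point for coverage that never falls below nominal. In the abatacept arm there is little to see: 18/45 gives 25.7–54.3% by Wald and 27.0–54.5% by Wilson. The choice should be fixed before unblinding.
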